Diagnosis and Main Inclusion Criteria	Unresectable Stage III and Stage IV melanoma who are positive for NRAS mutation or who are BRAF/NRAS WT and failed or are ineligible for standard treatment options
Study Product, Dose, Route, Regimen	CDX-3379 – ERBB3 human monoclonal antibody: 15mg/kg IV every three weeks Trametinib (Mekinist®) – MEK inhibitor: 2 mg PO daily

CONFIDENTIAL

Duration of administration	CDX-3379 infusion every three weeks and trametinib orally daily until disease progression, intolerable side effects, patient choice, or study closure
Reference therapy	
Phase 2 results of response rates will be compared to results from the NEMO trial for NRAS mutant melanoma – single agent MEK inhibitor (binimetinib) compared to DTIC – and WT melanoma to results from a phase I trial of trametinib in WT melanoma.
 
For Phase 2 exploratory objectives, PFS can be compared where PFS was 2.8 months for trametinib compared to 1.5 months for DTIC in NRAS mutant melanoma and PFS was 2 months for trametinib in WT melanoma.

Statistical Methodology	
Phase 1b: Safety run in of the combination of CDX-3379 and trametinib and monitored for DLTs. If DLT occurs in 2 or more participants, then de-escalated cohorts will be evaluated. Six to 18 evaluable participants will be treated to identify the MTD/RP2D prior to advancing to phase 2.
 
Phase 2: There are two Arms of the study – Arm A: NRAS mutant melanoma patients, and Arm B: WT melanoma patients. This is the first part of a Simon Minimax design. Each Arm will initially enroll 19 patients. If, after the 19 patients in each cohort, there are two or fewer responses, the cohort will be stopped. Otherwise, the study will be amended to accrue a total of 36 to each arm (an additional 17 participants per arm). If a true response rate is 0.20, we will have a probability of 0.46 of stopping early and a probability of 0.90 of deciding that the treatment is useful.

CONFIDENTIAL

1 Introduction

This document is a protocol for a human research study. This study is to be conducted in accordance with US government research regulations, and applicable international standards of Good Clinical Practice, and institutional research policies and procedures.

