If two or more of the six subjects experience DLT, we will consider the initial dose cohort beyond the MTD and we will enroll six more patients in cohort 1A or 1B, based on the toxicity pattern observed that is felt to be attributed to a particular drug. Dose reduction to -1A or -2A is specifically for toxicity related to trametinib, LVEF reduction, RPED, pneumonitis and LFT abnormalities. -1A is the first reduction, followed by -2A as the second reduction. For all other observed toxicities the default dose-reduced cohort is -1B followed by -2B. In the new dose cohort, if none or one patient experiences a DLT, then the study will open to full enrollment on the Phase II portion of the trial. If two or more of these additional six patients experience DLT, we will then enroll six

CONFIDENTIAL

additional patients at additional dose de-escalation cohorts, to be determined by sponsor (NYULMC) and NYU DSMC), again based on toxicity pattern observed and drug attribution. If two or more patients experience DLT at this new dose cohort, then the trial will be terminated.

Phase 2: There are two Arms - Arm A (*NRAS* mutant melanoma patients) and Arm B (WT melanoma patients). This is the first part of a Simon Minimax design. Each arm will initially enroll 19 subjects. If there are three or fewer responses, then accrual to that cohort will be stopped. Otherwise, the study will be amended to enroll a total of 36 subjects to each approved arm/cohort.

Abbreviations: C = cycle; D = day; PD = progressive disease.

Figure 2: Phase II study design

Translational Research -

We will perform biopsies on all phase Ib patients (expected 6 patients, but could be up to 18) and five patients on each Arm of the study for Phase II. Biopsies will be obtained pre-treatment, on-treatment between day 14-16, and at the time of disease progression. Archival tissue will also be collected. We will investigate pathway inhibition of ERBB3 signaling and MAPK signaling pathways by analyzing components of the signaling pathways in addition to key components integral in these signaling pathways. We will also evaluate NRG1/HRG1 (neuregulin 1/heregulin 1, ERBB3 ligand) expression and correlate this with treatment response.

CONFIDENTIAL

This material is the property of the NYU School of Medicine and Langone Medical Center. Do not disclose or use except as authorized in writing by the study sponsor

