7.1 Sample Size Determination

For Phase 1b:

No data are available for the combination of CDX-3379 (ERBB3 antibody) and trametinib. Six subjects will be enrolled at an initial dose level – a safety run-in - and monitored for DLTs. In these six subjects, if none or one subject experiences a DLT, then dose cohort 1 will be considered the RP2D, and phase II of the clinical trial will proceed. If two or more of the six subjects experience DLT, we will consider the initial dose cohort beyond the MTD and we will enroll six more subjects on a de-escalated cohort, based on toxicity pattern observed attributed to a particular drug (Cohort -1A or -1B). In this new dose cohort, if none or one subject experiences a DLT, then the study will open to full enrollment on the Phase II portion of the trial. If two or more of these additional six subjects experience DLT, we will then enroll six additional subjects at an additional dose de-escalation cohort -2, to be determined by sponsor (NYUL Health) and DSMC), again based on toxicity pattern observed and drug attribution. If two or more subjects experience DLT at this new dose cohort, then the trial will be terminated.

For Phase 2: There are two Arms - Arm A (*NRAS* mutant melanoma participants) and Arm B (WT melanoma participants). This is the first part of a Simon Minimax design. Each Arm will initially enroll 19 patients. If there are two or fewer responses, the specific cohort will be stopped. Otherwise, the study will be amended to enroll a total of 36 patients to each approved Arm/cohort (an additional 17 patients per arm). If a true response rate is 0.20, we will have a probability of 0.46 of stopping early and a probability of 0.90 of deciding that the treatment is useful.

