7.2 Statistical Methods

Data collection will begin from time of enrollment and subjects will be followed until death (PFS and OS endpoints). If subjects are still alive, they will be censored at the time of evaluation. We will first investigate the association between biomarker expression and disease characteristics using t-test, ANOVA, or Chi-squared tests. We will then investigate the association between biomarker expression and PFS and OS using Kaplan-Meier approach and log rank test where biomarker expression is dichotomized. We may also use Cox proportional models to assess the association between biomarkers and outcome with adjustment for potential confounders such as disease characteristics. Biomarkers measured pre-, on-and post-treatment will be examined and are mainly exploratory at this time. Future tests will be derived from these results. For phase 2, the primary efficacy endpoint, response rate, will be compared with the historically reported response rate for the single agent trametinib in *NRAS* mutant and *BRAF/NRAS* WT melanoma. For secondary endpoints, we will estimate median PFS, OS and 95% CI using the Kaplan-Meier approach. In *NRAS* mutant melanoma patients treated with single agent MEK inhibitor, response rate was 15% and median PFS was 2.8 months¹⁵, and in *BRAF/NRAS* WT melanoma

CONFIDENTIAL

patients treated with single agent MEK inhibitor, response rate was 10% and median PFS was 2 months⁷

Assuming a true response rate of 0.20, Simon's two-stage Minimax design will test the null hypothesis that $RR \leq 0.20$; the sample size of 36 patients provides an alpha level of 0.10 and power of 0.80. Nineteen patients will be enrolled to the *NRAS* mutant arm of the study and 19 patients will be enrolled to the BRAF/*NRAS* WT arm of the study in the phase 2. If at least 3 patients respond (PR or better) out of 19 evaluable patients, then the study will be amended to enroll an additional 17 patients (for a total of 36 evaluable patients). If the Simon two-stage Minimax design is fully completed, a minimum of 10 patients must demonstrate a response (PR or better) to reject the null hypothesis.

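### Rejecting a response rate of 0.20 or less with 10 of 36 responses has an exact type I error of about 0.16, not the stated 0.10; a cut-off of 11 is needed

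*Combined protocol and SAP*

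**What the plan says.** Section 7.2 sets up a Simon two-stage minimax test, in each arm, of a response rate of 0.20 or less. It states that "the sample size of 36 patients provides an alpha level of 0.10 and power of 0.80". The first stage is 19 patients per arm, and expansion follows a simple rule: "If at least 3 patients respond (PR or better) out of 19 evaluable patients, then the study will be amended" to add 17 patients, making 36. The final decision rule is that "a minimum of 10 patients must demonstrate a response (PR or better) to reject the null hypothesis".

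The first-stage boundary is not the same everywhere:

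- Section 7.1: "If there are two or fewer responses, the specific cohort will be stopped".
- Study Summary, Statistical Methodology: "there are two or fewer responses, the cohort will be stopped".
- Section 3.1: "If there are three or fewer responses, then accrual to that cohort will be stopped".

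The Study Summary and section 7.1 also give a probability of 0.46 of stopping early and 0.90 of judging the treatment useful, both attached to a true rate of 0.20. No section gives the alternative response rate.

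**The concern.** A Simon design is usually reported by two numbers, the largest counts that do *not* pass each stage. A design written as 10/36 therefore rejects with 11 or more responses. Section 7.2 rejects with 10 or more, which suggests that the boundary was read as the success count. If so, the test is more liberal than the plan says.

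This is the success rule for the phase 2 primary efficacy endpoint, applied separately in the *NRAS*-mutant and wild-type arms. Under the text as written, an arm that finishes at exactly 10 of 36 is declared a success, although that result is not significant at the stated level.

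**Working it through.** **Inputs, all from section 7.2 unless noted.** Null rate p0 = 0.20; stated alpha 0.10 (one-sided by the form of the null); n1 = 19; n2 = 17; n = 36; reject with k = 10 or more. First-stage boundary r1 (stop at r1 or fewer): 2 in the Study Summary and sections 7.1 and 7.2; 3 in section 3.1.

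**Formula.** The probability of rejecting at a true rate p is

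R(p) = Σ over x1 > r1 of P(X1 = x1) × P(X2 ≥ k − x1), with X1 ~ Bin(19, p) and X2 ~ Bin(17, p).

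**Does the stated alpha reproduce?** Terms at p = 0.20:

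| x1 | P(X1 = x1) | P(X2 ≥ 10 − x1) | product, k = 10 | P(X2 ≥ 11 − x1) | product, k = 11 |
|---|---|---|---|---|---|
| 3 | 0.2182 | 0.0377 | 0.0082 | 0.0109 | 0.0024 |
| 4 | 0.2182 | 0.1057 | 0.0231 | 0.0377 | 0.0082 |
| 5 | 0.1636 | 0.2418 | 0.0396 | 0.1057 | 0.0173 |
| 6 | 0.0955 | 0.4511 | 0.0431 | 0.2418 | 0.0231 |
| 7 | 0.0443 | 0.6904 | 0.0306 | 0.4511 | 0.0200 |
| 8 | 0.0166 | 0.8818 | 0.0147 | 0.6904 | 0.0115 |
| 9 | 0.0051 | 0.9775 | 0.0050 | 0.8818 | 0.0045 |
| 10 or more | | | 0.0016 | | 0.0016 |

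Summing from x1 = 3 gives the rule that stops at two or fewer; summing from x1 = 4 gives the rule that stops at three or fewer. The totals below are from unrounded terms.

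| Final cut-off | Stop at ≤2/19 | Stop at ≤3/19 | No interim stop |
|---|---|---|---|
| ≥10 of 36 | 0.1657 | 0.1575 | 0.1676 |
| ≥11 of 36 | 0.0885 | 0.0861 | 0.0889 |

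The stated 0.10 is not reached with a cut-off of 10 under any of these readings. The smallest cut-off that holds it is 11. The gap between the rows is the chance of continuing and finishing at exactly 10 responses: 0.1657 − 0.0885 = 0.077, or 0.1575 − 0.0861 = 0.071.

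**Where the 10 may come from.** This step needs an alternative rate that the documents do not give. With p1 = 0.40 and power 0.90 assumed, and alpha at most 0.10, a minimax search returns 19 patients, stop at three or fewer, 36 in total, reject at 11 or more. That design has alpha 0.0861, power 0.902 and early-stopping probability 0.455 at p0. It matches the protocol's 19, 36, 0.46 and 0.90. In Simon's notation it is 3/19, 10/36, where 10 is the largest total that does not reject. With power 0.80, which section 7.2 states, and p1 = 0.40, the search returns 14 then 24 patients, which does not match. The off-by-one reading is therefore likely but not proven.

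**Early stopping.** P(X1 ≤ 2) = 0.237 and P(X1 ≤ 3) = 0.455 at p = 0.20. The printed 0.46 belongs to stopping at three or fewer.

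**Power at assumed alternatives.** Each cell shows cut-off 10, then cut-off 11.

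| True rate | Stop at ≤2/19 | Stop at ≤3/19 |
|---|---|---|
| 0.30 | 0.670 → 0.532 | 0.651 → 0.523 |
| 0.36 | 0.884 → 0.801 | 0.869 → 0.792 |
| 0.40 | 0.953 → 0.909 | 0.944 → 0.902 |

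**The case against.** The arithmetic is not in dispute; the case on the other side is about weight and remedy.

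- **The rule is contingent.** This version enrols 19 per arm. The 36-patient stage exists only if an arm passes its first stage and the protocol is amended. That is true, but section 7.2 already prespecifies the final rule, and the amendment would carry it forward. Choosing between 10 and 11 after first-stage responses are known would be worse than settling it now.
- **A later analysis plan may change it.** Section 7.2 allows this, with major changes to the primary analysis also made by amendment. That is a route to a correction, not a correction.
- **The historical rates are lower.** Section 7.2 cites 15% and 10% for single-agent MEK inhibition. At those rates the rule of 10 or more rejects with probability of about 0.033 to 0.035 and 0.002. This limits the practical harm if those are the true rates, but the plan attaches its alpha to 0.20.
- **The stated aim is estimation.** The phase 2 primary objective is to estimate response rate and duration. The plan nevertheless adds a formal test with a success threshold.
- **Another input could be the misprint.** With a cut-off of 10, alpha is 0.098 or 0.093 for a null of 0.18. No section mentions that null. Keeping 10 and printing the true alpha would also remove the contradiction, but it would give up the stated error rate.

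**Conclusion.** The final rule in section 7.2 is wrong as written. Against the stated null of 0.20 its type I error is 0.166 or 0.157, about 1.6 times the stated 0.10. No reading of the first-stage rule repairs this. The conclusion rests only on the null, sample sizes and cut-off in section 7.2 and on exact binomial probabilities. It does not depend on the alternative rate or on how the error arose. The explanation of the cause, and every power figure, do depend on assumed alternatives.

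**What to change.** If the null of 0.20, alpha of 0.10 and 36 patients are kept, change the final rule in section 7.2 so that at least 11 of 36 responses are needed to reject, and say explicitly that 10 or fewer do not reject. The same edit should:

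1. Use one first-stage boundary in the Study Summary and sections 3.1, 7.1 and 7.2, and print its exact alpha. If stopping at two or fewer is kept, alpha is 0.0885, section 3.1 changes, and the 0.46 becomes 0.237. If stopping at three or fewer is kept, alpha is 0.0861, the 0.46 stands (0.455), and the other three places change.
2. State the alternative response rate with its exact power, and reconcile the 0.80 in section 7.2 with the 0.90 in the Study Summary and section 7.1, which is now attached to the null rate.

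If the sponsor finds that the null or the alpha is the misprinted input, the design must be restated with its exact operating characteristics.

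No patients are added. The cost is a bar one response higher and the loss of power tabulated above. With 11 responses required, 80% power needs a true rate of about 0.36 and 90% about 0.40. With 10 the corresponding rates are 0.33 to 0.34 and about 0.37. The change should be made before first-stage responses are known in either arm.

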7.3 Subject Population(s) for Analysis

All subjects enrolled on the study who are treated will have data collected at the pre-specified time points and this data will be subjected to the study analysis. Data analysis will be intention to treat, based on all subjects enrolled onto the study protocol.

8 Safety and Adverse Events

8.1 Definitions

Unanticipated Problems Involving Risk to Subjects or Others

Any incident, experience, or outcome that meets all of the following criteria:

- Unexpected in nature, severity, or frequency (i.e. not described in study-related documents such as the IRB-approved protocol or consent form, the investigators brochure, etc)
- Related or possibly related to participation in the research (i.e. possibly related means there is a reasonable possibility that the incident experience, or outcome may have been caused by the procedures involved in the research)
- Suggests that the research places subjects or others at greater risk of harm (including physical, psychological, economic, or social harm).

Adverse Event

An **adverse event** (AE) is any symptom, sign, illness or experience that develops or worsens in severity during the course of the study. Intercurrent illnesses or injuries should be regarded as adverse events.

Abnormal results of diagnostic procedures are considered to be adverse events if the abnormality:

- results in study withdrawal
- is associated with a serious adverse event
- is associated with clinical signs or symptoms
- leads to additional treatment or to further diagnostic tests
- is considered by the investigator to be of clinical significance

Serious Adverse Event

Adverse events are classified as serious or non-serious. A **serious adverse event** is any AE that is:

- fatal
- life-threatening

CONFIDENTIAL

- requires or prolongs hospital stay
- results in persistent or significant disability or incapacity
- a congenital anomaly or birth defect
- an important medical event

Important medical events are those that may not be immediately life threatening, but are clearly of major clinical significance. They may jeopardize the subject, and may require intervention to prevent one of the other serious outcomes noted above. For example, drug overdose or abuse, a seizure that did not result in in-patient hospitalization, or intensive treatment of bronchospasm in an emergency department would typically be considered serious.

All adverse events that do not meet any of the criteria for serious should be regarded as ***non-serious adverse events***.

Adverse Event Reporting Period

The study period during which adverse events must be reported is normally defined as the period from the initiation of any study procedures to the end of the study treatment follow-up. For this study, the study treatment follow-up is defined as 30 days following the last administration of study treatment.

Preexisting Condition

A preexisting condition is one that is present at the start of the study. A preexisting condition should be recorded as an adverse event if the frequency, intensity, or the character of the condition worsens during the study period.

General Physical Examination Findings

At screening, any clinically significant abnormality should be recorded as a preexisting condition. At the end of the study, any new clinically significant findings/abnormalities that meet the definition of an adverse event must also be recorded and documented as an adverse event.

Post-study Adverse Event

All unresolved adverse events should be followed by the investigator until the events are resolved, the subject is lost to follow-up, or the adverse event is otherwise explained. At the last scheduled visit, the investigator should instruct each subject to report any subsequent event(s) that the subject, or the subject's personal physician, believes might reasonably be related to participation in this study. The investigator should notify the study sponsor of any death or adverse event occurring at any time after a subject has discontinued or terminated study participation that may reasonably be related to this study. The sponsor should also be notified if the investigator should become aware of the development of cancer or of a congenital anomaly in a subsequently conceived offspring of a subject that has participated in this study.

Abnormal Laboratory Values

A clinical laboratory abnormality should be documented as an adverse event if any one of the following conditions is met:

- The laboratory abnormality is not otherwise refuted by a repeat test to confirm the abnormality
- The abnormality suggests a disease and/or organ toxicity
- The abnormality is of a degree that requires active management; e.g. change of dose, discontinuation of the drug, more frequent follow-up assessments, further diagnostic investigation, etc.

Abnormal lab values that are not clinically significant are not considered adverse events.

Hospitalization, Prolonged Hospitalization or Surgery

Any adverse event that results in hospitalization or prolonged hospitalization should be documented and reported as a serious adverse event unless specifically instructed otherwise in this protocol. Any condition responsible for surgery should be documented as an adverse event if the condition meets the criteria for and adverse event.

CONFIDENTIAL

Neither the condition, hospitalization, prolonged hospitalization, nor surgery are reported as an adverse event in the following circumstances:

- Hospitalization or prolonged hospitalization for diagnostic or elective surgical procedures for a preexisting condition. Surgery should **not** be reported as an outcome of an adverse event if the purpose of the surgery was elective or diagnostic and the outcome was uneventful.
- Hospitalization or prolonged hospitalization required to allow efficacy measurement for the study.
- Hospitalization or prolonged hospitalization for therapy of the target disease of the study, unless it is a worsening or increase in frequency of hospital admissions as judged by the clinical investigator.

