4.5.2 Data Collection and Follow-up for Withdrawn Subjects

When a subject is discontinued from treatment for any reason, they are to undergo the assessments in the end of treatment visit within 4 weeks of the last dose. All subjects who discontinue treatment as a result of an adverse event must be followed until resolution or stabilization of the adverse event. If a subject withdraws from study treatment, attempts should be made to contact the subject to determine the reason(s) for discontinuation. The subject will continue to be followed for survival information every 3 months after completion of the End of Treatment visit. All subjects, including subjects who discontinue treatment for other reasons than progressive disease per RECIST 1.1, should undergo a scan to assess disease status prior to termination from the study.

If a subject does not return to the clinic for the end of treatment visit or is not reached for overall survival follow-up, at least 3 documented attempts, including one via certified mail, should be made to contact the subject. If the subject does not respond to these requests, the date of death should be captured from public records.

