6.5 End of Treatment Visit

The end of treatment visit should be completed within 4 weeks of the last dose of the study drug. Vital signs, ECOG performance status, AE assessment and reporting, and disease evaluation should be performed. Blood will be drawn for CBC, chemistry, and PK. Progression tumor biopsy should be obtained within 4 weeks of last dose of study drug (last dose of study drug is calculated from the last dose of trametinib).

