6.6 Survival Follow-up

Survival data will be collected via telephone or clinic visits every 3 months (± 10 days) from the date of last treatment (date of last treatment is calculated from the last dose of trametinib) until death, loss to follow-up, withdrawal of consent, study termination by the Sponsor, or up to 5 years. In addition, any new anti-cancer therapies and procedures should be collected and documented. Should subjects refuse or drop out of survival follow-up, attempts should be made to obtain any death information via public records whenever possible.

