6.7 Schedule of Assessments Summary

Procedure	Screening	Cycle 1 ⁴			Cycle 2 ⁴			Additional cycle ⁴			Every 12 weeks or sooner, at the discretion of the physician	End of Treatment (EoT) ⁸	Survival Follow-up ¹²
		Wk 1	Wk 2	Wk 3	Wk 1	Wk 2	Wk 3	Wk 1	Wk 2	Wk 3			
Informed Consent	X												
Medical History	X												
Demographics	X												
Physical Exam	X	X	X		X	X		X				X	
Vital Signs	X	X			X			X				X	
ECOG PS	X	X			X			X				X	
CBC	X	X			X			X				X	
Serum Chemistry ¹³	X	X			X			X				X	
Tumor Biopsy	X												
	X												

CONFIDENTIAL

This material is the property of the NYU School of Medicine and Langone Medical Center. Do not disclose or use except as authorized in writing by the study sponsor

Baseline imaging within 4 weeks prior to enrollment (CT/PET-CT/MRI)													
Pregnancy Test (Urine)	X	X			X			X					
EKG	X	X ₁₁			X ₁₁			X ₁₁					
Archived tumor	X												
Fresh Core Biopsy	X ₂		X ₃	X ₃								X	
Pharmacokinetic blood samples		X ₁₀	X		X ₁₀	X		X				X	
Immunogenicity sample		X			X							X	
Concomitant meds	X	X	X		X			X				X	
CDX-3379 dosing ¹⁶		X			X			X					
Trametinib dosing		X	X	X	X	X	X	X	X	X			
AE assessment and reporting		X	X		X			X				X	
Disease evaluations ^{5,7}	X										X ₉	X ₁	
Overall Survival Reporting ⁶													X
Echocardiogram/MUGA ¹⁵	X										X		
Ophthalmologic Exam ¹⁴	X	X			X			X					

Footnotes:

- 1 = Unless performed in the prior 6 weeks as part of a previous visit
- 2= prior to first treatment with CDX-3379 and trametinib
- 3= performed between days 14-16
- 4= All procedures should occur ±2 calendar days from scheduled date of visit
- 5 = Disease evaluation per RECIST version 1.1.
- 6 = Should patients refuse or drop out of survival follow-up, attempts should be made to obtain any death information available via public records.
- 7 = Upon disease progression determination
- 8 = End of treatment visit should be completed within 4 weeks of the last dose of study drug
- 9 = end of treatment biopsy/disease progression. Should occur within 4 weeks of last treatment.
- 10 = PK blood samples are collected predose before CDX-3379, immediately following CDX-3379 infusion, and 1 hour post dose following trametinib
- 11= one reading prior to the start of CDX_3379 infusion
- 12= Survival data will be collected via telephone or clinic visits every 3 months (±10 days) from the date of last treatment until death, loss to follow-up, withdrawal of consent, or study termination by the Sponsor

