Deviations from the protocol must receive both Sponsor and the investigator's IRB approval before they are initiated. Any protocol deviations initiated without Sponsor and the investigator's IRB approval that may affect the scientific soundness of the study, or affect the rights, safety, or welfare of study subjects, must be reported to the Sponsor and to the investigator's IRB as soon as a possible, but **no later than 5 working days** of the protocol deviation.
- **Withdrawal of IRB approval**
An investigator shall report to the sponsor a withdrawal of approval by the investigator's reviewing IRB as soon as a possible, but **no later than 5 working days** of the IRB notification of withdrawal of approval.

Reporting to Celldex

Expedited reporting by investigator to Celldex. *Note that reporting to Celldex is required in addition to reporting to the FDA, as necessary, and does not replace the requirement to notify the FDA, if required.*

CONFIDENTIAL

- NYU will inform Celldex in writing using an SAE form or MEDWATCH 3500A form of any SAE within 24 hours of being aware of the event (see Section 8.1X for the definition of SAE). The written report must be completed and supplied to Celldex by facsimile within 24 hours/1 business day. The initial report must be as complete as possible, including an assessment of the causal relationship between the event and the investigational product(s), if available. Information not available at the time of the initial report (e.g., an end date for the adverse event or laboratory values received after the report) must be documented on a follow-up report.
- Completed SAE reports are to be submitted to:

Celldex Therapeutics, Inc.
Pharmacovigilance
[contact]
Email: [contact] (note-check for removal of HIPAA identifiers prior to sending information)

Reporting to Novartis

To ensure patient safety, every SAE, regardless of suspected causality, occurring after the patient has provided the main informed consent and until at least 30 days after the patient has stopped study treatment must be reported to Novartis within 24 hours of learning of its occurrence.

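### No adverse event check is scheduled at the end of the 30-day reporting window, so 2 to about 29 of the 30 days can fall after the last scheduled assessment

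*Combined protocol and SAP*

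**What the plan says.** **The window.** Section 8.1 defines the end of the AE reporting period: "For this study, the study treatment follow-up is defined as 30 days following the last administration of study treatment". Section 8.2 requires all AEs in that period to be recorded. For serious events reported to the trametinib supplier, whatever their suspected cause, 8.3.1 runs the period "until at least 30 days after the patient has stopped study treatment".

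**The last scheduled assessment.** In the 6.7 table the final mark in the AE row is under End of Treatment. Section 6.5 lists what is done there: "Vital signs, ECOG performance status, AE assessment and reporting, and disease evaluation should be performed". The timing appears in three places:
- 6.5: "The end of treatment visit should be completed within 4 weeks of the last dose of the study drug"
- 4.5.2, for patients who discontinue: "they are to undergo the assessments in the end of treatment visit within 4 weeks of the last dose"
- 6.7, footnote: "8 = End of treatment visit should be completed within 4 weeks of the last dose of study drug"

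None of the three gives an earliest day.

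**After that visit.** Section 6.6 states: "Survival data will be collected via telephone or clinic visits every 3 months", with a tolerance of 10 days either way, and adds new anti-cancer treatments and procedures. The Survival Follow-up column in 6.7 is marked only for overall survival.

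**Other duties that bear on the gap.** Section 8.2 obliges the investigator to ask about AEs at every contact. Sections 8.1 and 8.2 have unresolved events followed up, and 4.5.2 does the same for patients who stop because of an AE. Under 8.1, subjects are told at the last scheduled visit to report later events that they or their physician think may be related to the study.

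**The concern.** The obligation to collect runs to day 30, but the last scheduled occasion for collecting ends by day 28 and may come much earlier. A new event that starts between the two has no scheduled contact to pick it up. Because the visit day can differ between patients, the length of post-treatment observation differs too, and AE rates pooled over patients would mix unequal periods.

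At stake is the completeness of the safety description. Toxicity and tolerability are part of the phase Ib primary endpoint (3.2), and exposure does not stop with dosing. Section 1.2.2 gives trametinib a mean terminal half-life of 5.3 days. Section 1.1.1 says CDX-3379 was engineered for a longer half-life, with the effect predicted in humans.

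**Working it through.** The plan states no figure for this point, so there is none to reproduce. The check is day arithmetic.

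**Inputs**
- Window: W = 30 days after last administration (8.1).
- Day of the End of Treatment visit: v, at most 28 (4 weeks × 7 days; 4.5.2, 6.5, 6.7), with no lower limit.
- First survival contact: 3 months ± 10 days from last treatment (6.6), taking 3 months as 90 to 92 days.

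**Days of the window after the last scheduled AE assessment** = W − v

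| Visit day v | 30 − v | Share of window |
|---|---|---|
| 28 (latest allowed) | 2 | 2/30 = 6.7% |
| 14 | 16 | 16/30 = 53.3% |
| 1 | 29 | 29/30 = 96.7% |

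The day-14 row only illustrates the formula. The documents do not say when visits will fall.

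**Tolerance.** A 6.7 footnote reads "4= All procedures should occur ±2 calendar days from scheduled date of visit". Its marker sits on the cycle columns, while End of Treatment carries footnote 8. If it did apply, the latest visit would be 28 + 2 = day 30, leaving 30 − 30 = 0 days. It would permit that visit without requiring it.

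**Next scheduled contact.** Earliest: 90 − 10 = day 80. Latest: 92 + 10 = day 102. Relative to the close of the window, that is 80 − 30 = 50 to 102 − 30 = 72 days later, about 7 to 10 weeks.

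**Exposure still present at the visit**, taking the 5.3-day half-life as a single-exponential decline (an assumption): share remaining = 0.5^(v/5.3). This gives 87.7% at day 1, 16.0% at day 14 and 2.6% at day 28. An early visit therefore leaves a period with appreciable trametinib exposure and no scheduled AE check; a visit at day 28 leaves little.

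**Starting point of the 30 days.** Sections 6.5 (for the progression biopsy) and 6.6 count from the last trametinib dose. Section 8.1 refers to study treatment and names no drug. If the two drugs end on different days, the day on which the window closes is not fixed by the text.

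**The case against.** The strongest reply is that a reporting duty and a visit deadline do not contradict each other, and that the protocol has several safeguards.

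- **Questioning at each contact (8.2).** On its wording this includes the survival contacts. A reader might infer that the end of the window is never actively asked about; the documents do not support that. What remains is that the first such contact comes 50 to 72 days after the window closes, so it yields recall, and that 6.7 carries no AE mark there.
- **Follow-up of unresolved events.** This stands in full: a patient with an ongoing event at End of Treatment stays under follow-up. The gap is confined to new-onset events.
- **Spontaneous reports.** These help, but the instruction in 8.1 covers only events thought to be related, while the 30-day duty covers all AEs.

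A reader might also infer that patients who stop for toxicity have the earliest visit and the least observation. No section says so. Section 4.5.2 gives them follow-up to resolution or stabilization. For several toxicities trametinib is withheld for up to 3 or 4 weeks before permanent discontinuation (1.6.1.2.1), so the stopping decision, and the visit, may come late after the last dose.

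Nor should the 53% in the table be read as the average unobserved share. That would require visits spread evenly over days 0 to 28, which nothing in the documents supports.

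**Conclusion.** The mismatch is real and modest. The latest timely visit leaves 2 of the 30 days after the last scheduled AE assessment, and a visit on day 1 leaves 29. The 2-day minimum assumes that the ±2-day tolerance does not extend to End of Treatment; if it does, the minimum is 0, but the range above it is unchanged. How many events would be missed cannot be estimated from the documents.

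It would be tempting to carry this through to the dose decision, since toxicity is a phase Ib primary endpoint. The documents do not support that: the recommended dose rests on DLTs in a fixed 6-week period (3.1, 3.5), and the phase II decision rests on response counts. Neither depends on a day-30 contact. This is a cheap improvement to the collection of late, new-onset events.

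**What to change.** Keep the End of Treatment visit as it is and add a telephone check for AEs and SAEs at day 30 (for example +7 days) after the last dose of study treatment. Mark it in the AE row of the 6.7 table and state it in 6.5 and 4.5.2. A contact at day 30 or later leaves 0 of the 30 days uncovered.

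Two clarifications belong in the same amendment:
- State in 8.1 which drug's last dose starts the 30 days, and align 6.5 and 6.6 with it.
- Reconcile the Survival Follow-up column of 6.7 with the duty in 8.2 to ask about AEs at each contact.

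The cost is about one call per patient: 6 + 38 = 44 calls at the target enrollment in 4.4.1, and more if phase Ib or either arm is expanded. Moving the whole End of Treatment visit to day 30 or later is the weaker option. It would mean changing the 4-week limit in 4.5.2, 6.5 and 6.7, and it would also shift the disease evaluation and blood draws done at that visit.
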